4. RANDOMIZATION AND BLINDING

Patients eligible for enrollment into the study will fall into one of four cohorts:

Cohort 1 – 10-20 patients age 12-17 years of age with 10-30% body surface area (BSA) affected

Cohort 2 – 5-10 patients age 6-11 years of age with 10-30% body surface area (BSA) affected

Cohort 3 – 5-10 patients age 2-5 years of age with 10-30% body surface area (BSA) affected

Cohort 4 – 5-10 patients 6 months -1 year of age with 10-30% body surface area (BSA) affected

At Visit 1 eligible patients will be enrolled to the study and assigned a patient number.

Cohorts will be enrolled in sequential order. Each cohort will initiate enrollment once the previous cohort has reached the required number of patients and a safety analysis has been reviewed. Each cohort will be enrolled based on the availability of patients.

Each cohort will be reviewed for the potential of HPA axis suppression. If at least 50% of patients in each Cohort experience HPA axis suppression, enrollment for that cohort will be stopped and no further cohorts will be initiated. If at least 35% of patients have experienced HPA axis suppression across cohorts combined during the study, enrollment will be discontinued and no other cohorts will be initiated. Cohort 2 will not begin until safety data has been reviewed for Cohort 1. The same process will be followed for each Cohort until the study is complete.

The enrollment in the individual Cohort may not be required if the satisfactory safety data for the same age group was obtained in the study DSXS 1502.

5. SAMPLE SIZE

The sample size of 35 patients, stratified by age and % BSA, was determined to be sufficient.

6. STUDY ENDPOINTS

Primary Outcome Measures:

Hypothalamic Pituitary Adrenal (HPA) Axis Response to Cosyntropin demonstrating the absence or presence of adrenal suppression at the end of treatment

NOVUM PHARMACEUTICAL RESEARCH SERVICES
STATISTICAL ANALYSIS PLAN

Desoximetasone 0.15% Topical Spray

Protocol / Study No. DSXS 1502a / 71615002

Secondary Outcome Measures:

Hypothalamic Pituitary Adrenal (HPA) Axis Response to Cosyntropin demonstrating the presence of adrenal suppression at the end of treatment with % BSA as a covariate.

7. STATISTICAL ANALYSIS METHODS

If not otherwise specified, statistical significance is defined as $p < 0.05$ and is two-tailed. Data will be summarized with respect to demographic and baseline characteristics and safety variables.

For categorical variables, the number and percent of each category within a parameter will be calculated for non-missing data. For continuous variables, statistics will include n, mean, standard deviation, median, minimum and maximum values.

All statistical analyses will be conducted using SAS[®], Version 9.4 or higher. Datasets will be prepared using headings from Clinical Data Interchange Consortium (CDISC) Study Data Tabulation Model (SDTM) implementation for human clinical trials and ADaM (Analysis Dataset Model).

7.1 Baseline Characteristics

7.1.1 Subject Disposition

The subject accountability and disposition information will be summarized by study cohort. The number of subjects enrolled, treated with study medication will be tabulated by study cohort. In addition, completion status and primary reason for withdrawal will be summarized by study cohort.

7.1.2 Demographic and Other Baseline Characteristics

The cohorts will be compared for basic demographics (age, gender, ethnicity and race), baseline IGA, baseline EASI and baseline total BSA.

Summary tables by cohort will be presented. Continuous variables will be summarized using descriptive statistics (n, mean, standard deviation, median, minimum, maximum). Categorical variables will be summarized using frequencies and percentage.

Baseline comparability of the four cohorts will be presented using Chi-square test for the categorical variables, and Analysis of Variance for the continuous variables.

All data will be listed by cohort and patient.

7.1.3 Medical History

At Visit 1, patients will be questioned about medical history, including acute and chronic

NOVUM PHARMACEUTICAL RESEARCH SERVICES
STATISTICAL ANALYSIS PLAN

Desoximetasone 0.15% Topical Spray

Protocol / Study No. DSXS 1502a / 71615002

medical history and medical history relevant to their atopic dermatitis.

Medical history data will be listed by cohort and patient.

7.1.4 Concomitant Medications

At Visits 1-3, patients will be questioned about current and concomitant medication over the past 12 weeks.

All prior and concomitant medications taken since screening until the end of the study will be listed by cohort and patient.

7.1.5 Pregnancy Test

Urine pregnancy tests on women of child-bearing potential will be performed at Visits 1, 2, and 3.

Positive pregnancy test results will be listed by cohort and patient.

7.2 Safety Analysis of Potential HPA Axis Suppression

Dosing will be twice a day for 28 days excluding the doses prior to the Cortisol Response Test (54 applications). All patients who are enrolled, use at least 42 doses of the study drug and have data from a post-treatment cortisol response test will be included in the analysis. Patients who have not used 42 doses of the study drug will be excluded from the primary analysis of HPA axis suppression.

The primary analysis of interest is the proportion of patients in each group who are considered to have demonstrated possible HPA axis suppression following treatment with the study medication. As a secondary analysis of the data a logistic regression of the proportion of patients in the study with HPA axis suppression may be performed with %BSA affected as a covariate. This will depend on the distribution of the %BSA data collected.

The study will be enrolled by Cohort starting with Cohort 1 and each cohort will be reviewed for the potential of HPA axis suppression. If at least 50% of patients in Cohort 1 experience HPA axis suppression once the minimum number of patients has been enrolled and completed the cohort, enrollment for that cohort will be stopped and no further cohorts will be initiated. If at least 35% of patients have experienced HPA axis suppression across cohorts combined during the study, enrollment will be discontinued and no other cohorts will be initiated. Cohort 2 will not begin until safety data has been reviewed for Cohort 1. The same process will be followed for each Cohort until the study is complete.

For all patients the actual amount of desoximetasone (mg) applied during the study will be

NOVUM PHARMACEUTICAL RESEARCH SERVICES
STATISTICAL ANALYSIS PLAN

Desoximetasone 0.15% Topical Spray

Protocol / Study No. DSXS 1502a / 71615002

calculated from recorded bottle weights and presented.

7.3 Safety Analysis

Safety analysis will be conducted on all patients who applied at least one dose of study drug.

7.3.1 Adverse Events

All the adverse events (AEs) reported throughout the study will be coded and classified according to the MedDRA (Medical Dictionary for Regulatory Activities) coding dictionary (Version 19 or higher). Each adverse event is to be evaluated for date of start and end, seriousness, severity, causal relationship with the study drugs, action taken and outcome.

A summary table of the number and percent of patients with AEs by system organ class, preferred term, and cohort will be presented. Each patient will be counted only once within each preferred term.

A frequency summary table of the number of AEs by system organ class, preferred term, severity, and cohort will be presented. Severity will be classified as “Mild”, “Moderate”, or “Severe”.

Similarly, a frequency summary table of the number of AEs by system organ class, preferred term, and relationship to a study drug, and cohort will be presented. Relationship to a study drug will be classified as “Not Related” or “Related” where “Related” includes “Possible”, “Probable”, or “Definite”.

Should sufficient data exist, adverse event frequencies will be compared between cohorts using Fisher’s exact test.

All AEs will be listed by cohort and patient.

7.3.2 Vital Signs

The patient’s vital signs will be recorded (heart rate, blood pressure, temperature and respiration rate) at Visit 1, 2, and 3.

Abnormal vital signs will be listed by cohort and patient.

7.3.3 Laboratory Evaluations

At Visit 1 and Visit 3 a blood sample will be collected for hematology and clinical chemistry testing. The testing panel should include as a minimum the following tests:

Hematology

NOVUM PHARMACEUTICAL RESEARCH SERVICES
STATISTICAL ANALYSIS PLAN

Desoximetasone 0.15% Topical Spray

Protocol / Study No. DSXS 1502a / 71615002

- Hematocrit
- White blood cell count
- Platelets
- Hemoglobin
- Red blood cell count
- Differential white cell count

Chemistry

- Alkaline phosphatase
- Total bilirubin
- Alanine transaminase
- Creatinine
- Aspartate transaminase
- Glucose
- Blood urea nitrogen

Shift analysis using the categories; below, above and within the laboratory normal range will be performed to identify any specific laboratory parameter that shows a trend toward potentially clinically significant changes.

All data will be listed by cohort and patient.

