### **10.2 Safety Analysis**

Safety analysis will be conducted on all patients who applied at least one dose of study drug.

Adverse medical events experienced by the patients will be tabulated. The relationship of AEs, if any, to the study drug will be assessed by the Investigator. Adverse events assessed as definite, probable, possible or not related to the study drug will be presented. Shift analysis using the categories, below, above and within the laboratory normal range will be performed to identify any specific laboratory parameter that shows a trend toward potentially clinically significant changes.

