| Body System | MedDRA Term | Cohort | Related | Not Related |
|-------------------------------|--------------------|-----------------|----------------|--------------------|
| Patients with at least one AE | Total | Cohort 1 (N=xx) | xx (xx.x%) | xx (xx.x%) |
| | | Cohort 2 (N=xx) | xx (xx.x%) | xx (xx.x%) |
| | | Cohort 3 (N=xx) | xx (xx.x%) | xx (xx.x%) |
| | | Cohort 4 (N=xx) | xx (xx.x%) | xx (xx.x%) |
| Ear and labyrinth disorders | Ear pain | Cohort 1 (N=xx) | xx (xx.x%) | xx (xx.x%) |
| | | Cohort 2 (N=xx) | xx (xx.x%) | xx (xx.x%) |
| | | Cohort 3 (N=xx) | xx (xx.x%) | xx (xx.x%) |
| | | Cohort 4 (N=xx) | xx (xx.x%) | xx (xx.x%) |

N = Total number of events in each cohort; Percentage is based on total number of events.

Related = Possible, Probable, Definite

Created on: ddmmmyy hh:mm

Page 1 of N

**T16.1.9.13 Summary of Frequency of Serious Adverse Events
(Safety Population)**

| Body System | MedDRA Term | Cohort 1 N=xx | Cohort 2 N=xx | Cohort 3 N=xx | Cohort 4 N=xx |
|--|------------------------|--------------------------|--------------------------|--------------------------|--------------------------|
| Injury, poisoning and procedural complications | Alcohol poisoning | xx | xx | xx | xx |

Created on: ddmmmyy hh:mm

Page 1 of N

**T16.1.9.14 Summary of Shift Analysis of Clinical Laboratory Assessments (Chemistry) from Baseline to Day 28
(Safety Population)**

Alanine Aminotransferase (U/L)

| | Cohort 1 (N=xx) | | | Cohort 2 (N=xx) | | | Cohort 3 (N=xx) | | | Cohort 4 (N=xx) | | |
|------------|--------------------|---------------|---------------|--------------------|---------------|---------------|--------------------|---------------|---------------|--------------------|---------------|---------------|
| Baseline-> | Low | Normal | High |
| Endpoint | xx (xx.x%) | xx (xx.x%) | xx (xx.x%) |
| Low | xx (xx.x%) | xx (xx.x%) | xx (xx.x%) |
| Normal | xx (xx.x%) | xx (xx.x%) | xx (xx.x%) |
| High | xx (xx.x%) | xx (xx.x%) | xx (xx.x%) |

Table will continue for other lab parameters.

Similar table will be created for T16.1.9.18.

**T16.1.9.15 Summary of Shift Analysis of Clinical Laboratory Assessments (Hematology) from Baseline to Day 28
(Safety Population)**

**T16.1.9.16 Summary of Frequency of Pruritis Assessment
(Safety Population)**

| Visit | Score | Cohort 1 (N = xx) | Cohort 2 (N = xx) | Cohort 3 (N = xx) | Cohort 4 (N = xx) |

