|---------------|-----------------------|------------|--------------|-------------------|---------------------|---------------|
| Cohort 1 | XX-XXXX | XXX | 1 | Diastolic BP | XXX - XXX | XXX |
| | | | 2 | | | |
| | | | 3 | | | |

Cohort 2
Cohort 3
Cohort 4

Created on: ddmmmyy hh:mm

Page 1 of N

L16.2.8.3 Listing of Abnormal Physical Examination Results

| Cohort | Patient Number | Visit | System | Results |
|----------|----------------|-------|--------|-----------------|
| Cohort 1 | xx-xxxx | 1 | HEENT | Abnormal (Scar) |

2
3

Cohort 2
Cohort 3
Cohort 4

Created on: ddmmmyy hh:mm

Page 1 of N

L16.2.8.4 Listing of Clinical Hematology Laboratory Results

| Cohort | Patient Number | Visit | Hematocrit (unit) | WBC (unit) | Platelets (unit) | Hemoglobin (unit) | etc. |
|----------|----------------|--------|----------------------|---------------|---------------------|----------------------|------------|
| Cohort 1 | xx-xxxx | 1 3 | xxx xxx | xxx xxx | xxx xxx | xxx xxx (Low) | xxx xxx |

Cohort 2

Cohort 3

Cohort 4

Created on: ddmmmyy hh:mm

Page 1 of N

L16.2.8.5 Listing of Clinical Chemistry Laboratory Results

| Cohort | Patient Number | Visit | Alkaline Phosphatase (unit) | Alnine (unit) | Aspartate Transaminase (unit) | Blood Urea Nitrogen (unit) | etc. |
|----------|----------------|--------|--------------------------------|------------------|----------------------------------|-------------------------------|------------|
| Cohort 1 | xx-XXXX | 1 3 | XXX XXX | XXX XXX | XXX (High) XXX | XXX XXX | XXX XXX |

Cohort 2

Cohort 3

Cohort 4

Created on: ddmmmyy hh:mm

Page 1 of N

NOVUM PHARMACEUTICAL RESEARCH SERVICES
STATISTICAL ANALYSIS PLAN

Desoximetasone 0.15% Topical Spray

Protocol / Study No. DSXS 1502a / 71615002

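### The only laboratory summary is a by-cohort low/normal/high shift table with no Total column and no change from baseline, so a moderate systematic change would be poorly detected

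*SAP*

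**What the plan says.** On timing, SAP 7.3.3 states: "At Visit 1 and Visit 3 a blood sample will be collected for hematology and clinical chemistry testing". Each child therefore has a paired value for every parameter.

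Protocol 10.2 sets the method: "Shift analysis using the categories, below, above and within the laboratory normal range will be performed". SAP 7.3.3 repeats the method and shares the protocol's purpose; its sentence ends: "within the laboratory normal range will be performed to identify any specific laboratory parameter that shows a trend toward potentially clinically significant changes". Neither document says what pattern would count as a trend.

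The chemistry shell, T16.1.9.14 ("Summary of Shift Analysis of Clinical Laboratory Assessments (Chemistry) from Baseline to Day 28"), is a Low/Normal/High grid for Cohorts 1 to 4 side by side. It has no Total column and no row for a mean or a change. T16.1.9.15 (hematology) appears by title only.

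SAP 7.3.3 also says "All data will be listed by cohort and patient". The matching shells, such as "L16.2.8.4 Listing of Clinical Hematology Laboratory Results", show each patient's results at Visits 1 and 3, with Low and High flags.

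Vital signs are taken at Visits 1, 2 and 3. SAP 7.3.2 plans one output: "Abnormal vital signs will be listed by cohort and patient". It states no trend aim for them.

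SAP 7 says in general that safety variables will be summarized, and adds: "For continuous variables, statistics will include n, mean, standard deviation, median, minimum and maximum values". %BSA (T16.1.9.6) and EASI (T16.1.9.8) receive mean, SD, median and range by visit. Laboratory values and vital signs do not.

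**The concern.** A shift against normal limits registers only a child who crosses a limit. If most children move in the same direction but stay inside the range, the table barely changes. Splitting it into four small cohorts without a pooled column thins it further.

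The adverse event profile is a secondary objective, and the laboratory shifts belong to the safety analysis in Protocol 10.2. A nearly empty grid could be taken as evidence of no laboratory change when it had little chance of showing a moderate one. If pooled changes are worked out only after the listings have been read, the choice of parameters to report will not have been specified in advance.

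**Working it through.** **The plan's own figures.** Neither document gives a detectable change, an SD or a precision for laboratory data, so there is no laboratory figure to reproduce. The enrolment range is the sum of the cohort ranges: 10+5+5+5 = 25 and 20+10+10+10 = 50. The stated sample size of 35 (Protocol 10.1.1, SAP 5) comes with no inputs.

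**Assumptions (none from the documents).**
- Values are normal with SD 1 at both visits, and the normal range is mean ±1.96 SD.
- The correlation between visits is ρ = 0.5, varied to 0.8.
- The true mean rise is d = 0.5 SD.
- Cohorts are full, with no missing tests.

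**Step 1: chance that one child moves from Normal to High.** With X the Visit 1 value and Y the Visit 3 value, p = P(-1.96 < X < 1.96 and Y > 1.96), where Y has mean d. At ρ = 0.5 this gives p = 0.0629. With no mean change it is 0.0204. Across ρ = 0.5 to 0.8, p runs from 0.063 down to 0.054.

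The change has SD √(2(1-ρ)) = 1 at ρ = 0.5, so the chance that a child's value is higher at Visit 3 is Φ(0.5/1) = 0.69. About 69% of children rise, and about 6% cross into High.

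**Step 2: what the shift table would show, and what a change summary would show.** Expected moves are n × p. The chance of no move is (1-p)^n; for n = 5 this is 0.9371^5 = 0.72. The half-width of a 95% CI for the mean change is t(0.975, n-1) × √(2(1-ρ)) / √n; for n = 5 this is 2.776 × 1 / 2.236 = 1.24 SD.

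| n | where it applies | expected moves to High | chance of none | CI half-width for mean change (SD) |
|---|---|---|---|---|
| 5 | minimum, Cohorts 2-4 | 0.31 | 72% | 1.24 |
| 10 | maximum, Cohorts 2-4; minimum, Cohort 1 | 0.63 | 52% | 0.72 |
| 20 | maximum, Cohort 1 | 1.26 | 27% | 0.47 |
| 25 | pooled minimum | 1.57 | 20% | 0.41 |
| 35 | stated sample size | 2.20 | 10% | 0.34 |
| 50 | pooled maximum | 3.14 | 4% | 0.28 |

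**Step 3: sensitivity.** At ρ = 0.8 the chance of no move in a cohort of 5 is 76%. The CI half-width falls to 0.79 SD at n = 5, 0.45 at n = 10, 0.26 at n = 25 and 0.18 at n = 50. For a larger rise of 1 SD (ρ = 0.5), p = 0.1535, and the chance of no move is 0.8465^5 = 43% in a cohort of 5 and 1.6% in 25.

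**Reading.** For a 0.5 SD rise, a typical cohort of 5 shows no child moving into High. Pooled over 25 to 50 children the table shows about 2 to 3, against about 0.5 to 1 with no change. The pooled mean change has a half-width of 0.28 to 0.41 SD, narrower than the assumed 0.5 SD effect. Within one cohort of 5-10 the interval is wide even on the measured scale (0.72 to 1.24 SD at ρ = 0.5), so the Total column is needed as well as the change from baseline.

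**The case against.** The strongest reply is that the shift table suits the aim as written. The aim concerns changes of potential clinical significance, and normal limits are a natural yardstick for those. A small drift inside the range may not qualify. The SAP also follows the protocol's method, no decision in the study turns on laboratory means, and adrenal effect is tested directly by cosyntropin stimulation. All of this stands. It makes the point an improvement and not the correction of an error, and the shift tables should stay.

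A reader might infer that the trend aim cannot be met at all. The documents do not support that. Every laboratory value is listed, the four cohort counts can be added, and under the same assumptions at least one child moves into High in 80% of pooled samples of 25, 90% of 35 and 96% of 50. Larger changes show more readily. Nor are all cohorts of size 5-10: Cohort 1 has 10-20, which is 40% of patients at either end (10/25 and 20/50).

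A reader might also compare the power of a test on shifts with that of a paired test. The SAP plans no test on laboratory shifts, so such a comparison shows lost information but not a defect in a planned test.

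SAP 7's general rule could be read as already covering these variables, and SAP 8 says the shells may not reflect every aspect of the study. That is a fair reading of intent, but the specific sections name other outputs and nothing specifies change from baseline.

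Finally, neither document assigns any laboratory parameter or vital sign a role as a marker of systemic steroid exposure, and without a control arm a mean change could not be attributed to the drug. The point does not rest on either claim.

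**Conclusion.** The point holds as a low-priority improvement. The one planned laboratory summary is a weak tool for its stated purpose: it is categorical, split by cohort and unpooled, and the SAP's own rule for continuous variables is not carried through. Under the assumed 0.5 SD rise, ±1.96 SD range and correlation of 0.5, about 6% of children move into High and 72% of cohorts of 5 show none. These figures illustrate the loss and are not estimates for this trial; the documents supply no SD, correlation or expected change.

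The trend argument applies to laboratory values only. For vital signs the point is narrower: SAP 7 promises a summary of continuous safety variables, while SAP 7.3.2 lists only the abnormal values, so readings within the normal range appear in no planned table or listing.

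**What to change.** - **SAP 7.3.3:** add a table for each laboratory parameter giving n, mean, SD, median and range at Visits 1 and 3, and the within-patient change from Visit 1 with a 95% CI labelled as descriptive, by cohort and in a Total column.
- **T16.1.9.14 and T16.1.9.15:** keep the shift tables and add a Total column to each.
- **SAP 7.3.2:** apply the SAP 7 continuous summary to vital signs by visit, alongside the listing of abnormal values.

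The cost is some SAP wording and two or three standard tables, from data already collected. There are more tables to read. The intervals are unadjusted for the number of parameters, have no control group behind them, and say little within a single cohort of 5-10. The text should say so.

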7.3.4 Investigator Global Assessment

At each visit the Investigator will perform an Investigator Global Assessment (IGA).

Investigator Global Assessment will be summarized using frequency and percentage by cohort and visit.

Investigator Global Assessment will also be listed by cohort and patient.

7.3.5 Eczema Area and Severity Index Score (EASI)

Eczema Area and Severity Index Score will be assessed at each visit.

EASI will be summarized using frequency and percentage by cohort and visit. EASI will also be listed by cohort and patient.

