2. OBJECTIVES

1. The objective of this study is to evaluate the potential of desoximetasone 0.15% topical spray to suppress HPA axis function in patients with moderate to severe atopic dermatitis.
2. The secondary objectives are to evaluate the efficacy parameters and adverse event (AE) profiles of desoximetasone 0.15% topical spray administered to patients with moderate to severe atopic dermatitis.

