|-------------|---|------------|------------|------------|------------|------------|----------------|
| | | N=xx | N=xx | N=xx | N=xx | N=xx | |
| Age (years) | n | xx | xx | xx | xx | xx | x.XXXX |
| | Mean ± SD | xx.x ± x.x | |
| | Median | xx.x | xx.x | xx.x | xx.x | xx.x | |
| | Range | xx-xx | xx-xx | xx-xx | xx-xx | xx-xx | |
| Age Groups | <=1 | - | - | - | xx (xx.x%) | - | |
| | 2 – 5 | - | - | xx (xx.x%) | - | - | |
| | 6 – 11 | - | xx (xx.x%) | - | - | - | |
| | 12 – 17 | xx (xx.x%) | - | - | - | - | |
| | 18 – 40 | - | - | - | - | - | |
| | 41 – 64 | - | - | - | - | - | |
| | 65 – 75 | - | - | - | - | - | |
| | > 75 | - | - | - | - | - | |
| Race | American Indian or Alaska Native | xx (xx.x%) | x.XXXX |
| | Asian | xx (xx.x%) | |
| | Black/African American | xx (xx.x%) | |
| | Native Hawaiian or other Pacific Islander | xx (xx.x%) | |
| | White | xx (xx.x%) | |
| | Other | xx (xx.x%) | |
| Ethnicity | Hispanic or Latino | xx (xx.x%) | x.XXXX |
| | Not Hispanic or Latino | xx (xx.x%) | |

N= number of patients in the cohort; n= number of patients with data available; % is based on N

**T16.1.9.3 Summary of Demographic Data
(Safety Population)**

| | n | Cohort 1 | Cohort 2 | Cohort 3 | Cohort 4 | Total | P-value |
|--------------------|--------------|------------|------------|------------|------------|------------|---------|
| | | N=xx | N=xx | N=xx | N=xx | N=xx | |
| Baseline Total BSA | n | xx | xx | xx | xx | xx | x.XXXX |
| | Mean ± SD | xx.x ± x.x | |
| | Median | xx.x | xx.x | xx.x | xx.x | xx.x | |
| | Range | xx-xx | xx-xx | xx-xx | xx-xx | xx-xx | |
| Baseline IGA | Clear | xx (xx.x%) | x.XXXX |
| | Almost Clear | xx (xx.x%) | |
| | Mild | xx (xx.x%) | |
| | Moderate | xx (xx.x%) | |
| | Severe | xx (xx.x%) | |
| EASI | n | xx | xx | xx | xx | xx | x.XXXX |
| | Mean ± SD | xx.x ± x.x | |
| | Median | xx.x | xx.x | xx.x | xx.x | xx.x | |
| | Range | xx-xx | xx-xx | xx-xx | xx-xx | xx-xx | |

N= number of patients in the cohort; n= number of patients with data available; % is based on N

T16.1.9.4 Summary of Patients Randomized, Included in Safety Analysis of Potential HPA Axis Suppression by Study Center

| Site No. | PI Name | Total | | Cohort 1 | | Cohort 2 | | Cohort 3 | | Cohort 4 | |
|----------|---------|------------|------------|------------|-----------|------------|-----------|------------|-----------|------------|-----------|

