| Visit | Score | Cohort 1 (N = xx) | Cohort 2 (N = xx) | Cohort 3 (N = xx) | Cohort 4 (N = xx) |
|-------|-------------------------|----------------------|----------------------|----------------------|----------------------|
| 1 | 0 (Clear) | xx (xx.x%) | xx (xx.x%) | xx (xx.x%) | xx (xx.x%) |
| | 1 (Almost Clear) | xx (xx.x%) | xx (xx.x%) | xx (xx.x%) | xx (xx.x%) |
| | 2 (Mild Disease) | xx (xx.x%) | xx (xx.x%) | xx (xx.x%) | xx (xx.x%) |
| | 3 (Moderate Disease) | xx (xx.x%) | xx (xx.x%) | xx (xx.x%) | xx (xx.x%) |
| | 4 (Severe Disease) | xx (xx.x%) | xx (xx.x%) | xx (xx.x%) | xx (xx.x%) |
| 2 | 0 (Clear) | xx (xx.x%) | xx (xx.x%) | xx (xx.x%) | xx (xx.x%) |
| | 1 (Almost Clear) | xx (xx.x%) | xx (xx.x%) | xx (xx.x%) | xx (xx.x%) |
| | 2 (Mild Disease) | xx (xx.x%) | xx (xx.x%) | xx (xx.x%) | xx (xx.x%) |
| | 3 (Moderate Disease) | xx (xx.x%) | xx (xx.x%) | xx (xx.x%) | xx (xx.x%) |
| | 4 (Severe Disease) | xx (xx.x%) | xx (xx.x%) | xx (xx.x%) | xx (xx.x%) |

3

Created on: ddmmmyy hh:mm

Page 1 of N

**T16.1.9.8 Summary of Total Score - Eczema Area and Severity Index (EASI)
(Safety Population)**

| Visit | Statistic | Cohort 1 (N = xx) | Cohort 2 (N = xx) | Cohort 3 (N = xx) | Cohort 4 (N = xx) |
|-------|---------------|----------------------|----------------------|----------------------|----------------------|
| 1 | n | xx | xx | xx | xx |
| | Mean \pm SD | xxx.x \pm xx.x | xxx.x \pm xx.x | xxx.x \pm xx.x | xxx.x \pm xx.x |
| | Median | xxx.x | xxx.x | xxx.x | xxx.x |
| | Range | xxx - xxx | xxx - xxx | xxx - xxx | xxx - xxx |
| 2 | | | | | |
| 3 | | | | | |

Created on: ddmmmyy hh:mm

Page 1 of N

**T16.1.9.9 Overall Summary of Adverse Events
(Safety Population)**

| Description | Cohort 1 | Cohort 2 | Cohort 3 | Cohort 4 | Total |
|---|-----------------|-----------------|-----------------|-----------------|--------------|
| | N=xx | N=xx | N=xx | N=xx | N=xx |
| Patients Randomized | xxx | xxx | xxx | xxx | xxx |
| Patients with at least one AE | xx (xx.x%) | xx (xx.x%) | xx (xx.x%) | xx (xx.x%) | xx (xx.x%) |
| Discontinued study drug due to above AE | xx (xx.x%) | xx (xx.x%) | xx (xx.x%) | xx (xx.x%) | xx (xx.x%) |
| | | | | | |
| AEs reported | xxx | xxx | xxx | xxx | xxx |
| Mild | xx (xx.x%) | xx (xx.x%) | xx (xx.x%) | xx (xx.x%) | xx (xx.x%) |
| Moderate | xx (xx.x%) | xx (xx.x%) | xx (xx.x%) | xx (xx.x%) | xx (xx.x%) |
| Severe | xx (xx.x%) | xx (xx.x%) | xx (xx.x%) | xx (xx.x%) | xx (xx.x%) |

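### SAP 7.3.5 plans a frequency table for EASI, against the SAP's own rule and shell, and nothing plans within-patient change in EASI or %BSA affected

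*SAP*

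**What the plan says.** SAP 2 includes efficacy among its aims: "The secondary objectives are to evaluate the efficacy parameters". The protocol's objectives agree. SAP 6 names no efficacy endpoint; its only secondary outcome is "Hypothalamic Pituitary Adrenal (HPA) Axis Response to Cosyntropin demonstrating the presence of adrenal suppression at the end of treatment with % BSA as a covariate".

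For EASI, SAP 7.3.5 gives the method in one sentence: "EASI will be summarized using frequency and percentage by cohort and visit". The general rule in SAP 7 is different: "For continuous variables, statistics will include n, mean, standard deviation, median, minimum and maximum values". Shell T16.1.9.8 follows the general rule, with n, mean ± SD, median and range by cohort at Visits 1, 2 and 3. T16.1.9.3 treats baseline EASI the same way.

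For %BSA affected, SAP 7.3.6 and T16.1.9.6 give descriptive statistics by cohort and visit. There text and shell agree, but again each visit stands alone. The schedule collects EASI and %BSA affected at Visits 1, 2 and 3.

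**The concern.** There are two linked defects.

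First, the text and the shell give different instructions for the same variable. The SAP defines no EASI bands, so a literal frequency table would have to list raw scores.

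Second, following the shell still does not produce the quantity that the efficacy objective needs. There is one treatment and no control, so the available evidence on efficacy is how far each child moved from his or her own baseline. A table of separate visit summaries discards the pairing. It does not show the spread of individual changes, and it gives no basis for an interval around the mean change. If any child has no end-of-study assessment, the Visit 1 and Visit 3 columns also describe different sets of children.

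**Working it through.** **1. The scale.** SAP Appendix B states a maximum of 72. Four signs scored up to 3 give 12, and the area score goes up to 6. So 12 × 6 × (0.1 + 0.2 + 0.3 + 0.4) = 72, and with the weights for ages 0-7, 12 × 6 × (0.2 + 0.2 + 0.3 + 0.3) = 72. The stated maximum is reproduced. Entry requires at least 15, so baseline can take at most 72 − 15 + 1 = 58 whole-number values, before any narrowing by the 30% limit on affected BSA. Cohorts have 5-10 or 10-20 children, so a frequency table of raw scores would be close to one child per row.

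**2. The instructions side by side.**

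| Place | EASI summary |
|---|---|
| SAP 7.3.5 | frequency and percentage |
| SAP 7, continuous variables | n, mean, SD, median, minimum, maximum |
| Shell T16.1.9.8 | n, mean ± SD, median, range |
| Shell T16.1.9.3 (baseline) | n, mean ± SD, median, range |

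The 7.3.5 sentence is the odd one out.

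**3. Is change planned anywhere?** No text or shell in either document gives change or percent change from Visit 1 for EASI or %BSA affected. The only baseline-to-endpoint analysis is the laboratory shift analysis (SAP 7.3.3, T16.1.9.14 and T16.1.9.15).

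**4. What visit summaries leave open.** The data here are assumed, for illustration: five children with Visit 1 scores 16, 18, 20, 22, 24.

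| | Visit 3, same order | Visit 3 mean (SD) | Changes | Mean change (SD) |
|---|---|---|---|---|
| A | 6, 8, 10, 12, 14 | 10 (3.16) | all −10 | −10 (0) |
| B | 14, 12, 10, 8, 6 | 10 (3.16) | −2, −6, −10, −14, −18 | −10 (6.32) |

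Visit 1 is mean 20, SD 3.16 in both. The Visit 3 values are the same five numbers, so every row of T16.1.9.8 is identical for A and B. With complete data the mean change can be recovered by subtraction, but its spread cannot, and so neither can a confidence interval.

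In general, with equal visit SDs (assumption), SD of change = SD × √(2(1 − ρ)):

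- ρ = 0: 1.41 × SD
- ρ = 0.3: 1.18 × SD
- ρ = 0.5: 1.00 × SD
- ρ = 0.8: 0.63 × SD

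The documents give no correlation, and T16.1.9.8 would not reveal it.

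**5. One missing Visit 3 value.** Assumed data: baseline 16, 18, 20, 22, 40; Visit 3 values 10, 12, 14, 16, with the child at 40 missing.

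- Visit 1 mean = 116/5 = 23.2; Visit 3 mean = 52/4 = 13.0; difference = −10.2.
- Paired change in the four with both values = 13.0 − 76/4 = 13.0 − 19.0 = −6.0.

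The gap of 4.2 points comes entirely from comparing different children. The paired figure says nothing about the child at 40.

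**The case against.** **Attrition may be small.** Protocol 9.3.4 asks for all end-of-study procedures at the last visit of a child who leaves early. Protocol 11.2.4 has the Visit 3 case report form completed for early terminators, and the schedule combines the two visits. A child who withdraws for worsening dermatitis should therefore have an end-of-study EASI. This stands: the mismatch in step 5 arises only for children with no such assessment, for instance those lost to follow-up. T16.1.9.8 also prints n, so any loss would be visible. The point in step 4 does not depend on attrition.

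**The shells are provisional and the study is about safety.** SAP 8 allows the shells to be modified, and EASI sits under the safety analysis. But 7.3.5 is SAP text, not a shell, and efficacy is still a stated objective.

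**A reader might infer that the efficacy objective is never answered.** The documents do not support that. Every eligible child enters at IGA 3 or 4, so an IGA of 0 or 1 at Visit 3 in T16.1.9.7 implies an improvement of at least two grades. EASI and %BSA affected are also listed by patient. What is missing is a planned summary of change in these two measures.

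**A reader might also infer that the IGA and pruritus percentages have two conflicting denominators.** SAP 7 says "the number and percent of each category within a parameter will be calculated for non-missing data", while one footnote reads "N= number of patients in the cohort; n= number of patients with data available; % is based on N". That footnote belongs to T16.1.9.3, the demographic and baseline table. For the by-visit IGA and pruritus tables, the non-missing rule is the only one stated. T16.1.9.8 contains no percentages, so denominators have no part in the missing change summary.

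**Conclusion.** The point holds in two parts. The contradiction between SAP 7.3.5 and both SAP 7 and T16.1.9.8 is plain on the page. The absence of any planned within-patient change for EASI or %BSA affected is equally clear, and it leaves an avoidable gap in a stated secondary objective.

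The documents cannot fix the size of the effect. The figures in working steps 4 and 5 rest on assumed data and show what the planned table cannot distinguish; they do not predict this trial. With complete data only the spread and the interval are lost. With missing end-of-study values, the mean change is distorted as well.

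This is an inexpensive improvement to a secondary, descriptive analysis and leaves the primary analysis of adrenal suppression untouched. Paired change restores the pairing but covers only children with both values, so dropout bias remains. Without a control group it also cannot separate a drug effect from natural improvement or regression to the mean after entry at EASI 15 or more.

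**What to change.** Replace the 7.3.5 sentence with wording such as: *EASI will be summarised by cohort and visit with n, mean, SD, median and range. Change from Visit 1 at Visits 2 and 3 will be summarised, by cohort and overall, in patients with both values, with the number of pairs, the same statistics and a descriptive 95% confidence interval.* Add the second sentence, adapted, to 7.3.6 for %BSA affected.

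In T16.1.9.8 and T16.1.9.6, add the change rows at Visits 2 and 3 and an overall column. State that the intervals are descriptive (they will be wide with 5-20 children per cohort), and that the summary uses available pairs and does not correct for dropout.

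The cost is two edited paragraphs and extra rows and a column in two existing shells. The data are already collected at Visits 1-3. The change should be made before database lock, by which time Protocol 10.1 requires the SAP to be final.
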